## **ABSTRACT**

**OBJECTIVE:** To test the hypothesis that a feeding-bundle concurrent with acid-suppression is superior to acid-suppression alone in improving gastroesophageal reflux disease (GERD) attributed-symptom scores and feeding outcomes in neonatal ICU infants.

**METHODS:** Infants (N=76) between 34-60 weeks' postmenstrual age with acid reflux index>3% were randomly allocated to study (acid suppressive therapy + feeding bundle) or conventional (acid suppressive therapy only) arms for 4 weeks. Feeding bundle included: total fluid volume <140 ml/kg/day, fed over 30 min in right lateral position, and supine postprandial position. Primary outcome was independent oral feeding and/or  $\geq 6$ -point decrease in symptom score (I-GERQ-R). Secondary outcomes included growth (weight, length, head circumference), length of hospital stay (LOHS, days), airway (oxygen at discharge), and developmental (Bayley scores) milestones.

**RESULTS:** Of 688 screened: 76 infants were randomized and used for the primary outcome as intent-to-treat, and secondary outcomes analyzed for 72 infants (N=35 conventional, N=37 study). For study vs conventional groups, respectively: a) 33%(95% CI, 19%-49%) vs 44%(95% CI, 28%-62%), p=0.28 achieved primary outcome success, and b) secondary outcomes did not significantly differ (p>0.05).

**CONCLUSIONS:** Feeding strategy modifications concurrent with acid suppression are not superior to PPI alone in improving GERD symptoms or discharge feeding, short-term and long-term outcomes.

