## STUDY OUTCOMES

### Primary and Secondary Clinical Outcomes

The clinically meaningful primary and secondary outcomes did not differ significantly between groups (**Table 2**). I-GERQ-R scores for study and conventional groups are shown (**Fig 2**). At inception: positive I-GERQ-R was 19/35 (54%) in the conventional group vs 24/37 (65%) in the study group,  $p=0.36$ . At Time-2: positive I-GERQ-R prevalence was 9/31 (29%) in the conventional group vs 13/34 (38%) in the study group,  $p=0.43$ . In the study group vs conventional group, respectively: a) primary outcome achieved in 33% (95% CI, 19% - 49%) vs 44% (95% CI, 28% - 62%) ( $p=0.28$ ), b) secondary outcomes: independent oral feeding in 65% (95% CI, 48% - 80%) vs 77% (95% CI, 60% - 90%),  $p=0.26$ ,  $\geq 6$ -point I-GERQ-R decrease in 38% (95% CI, 22% - 56%) vs 35% (95% CI, 19% - 55%),  $p=0.82$ , length of stay was 98 [81-132] days vs 108 [83-125] days,  $p=0.89$ , and oxygen requirement at discharge in 19% (95% CI, 8% - 35%) vs 26% (95% CI, 13% - 43%),  $p=0.49$ . There were no significant differences in growth metrics (all  $p>0.05$ ) or developmental scores at 2 years (all  $p>0.05$ ). Feeding outcomes or I-GERQ-R scores did not significantly differ between conventional vs study groups based on feeding method at inception (**Table 3**). Individual I-GERQ-R questions relating to vomiting, regurgitation, and crying (i.e. frequency of emesis, volume of emesis, symptoms with emesis, and crying more than usual in the

past week) had no differences ( $P>0.05$ ) within the group or between the groups across maturation for these individual symptoms, except for symptoms with emesis (never: rarely: sometimes: often: always, %) was 16:16:42:19:6 for conventional group at Time-1 vs 18:18:29:0:35 for study group at Time-1,  $p < 0.01$ .

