**Table 2. Primary and Secondary Clinical Outcomes and Compliance Measures**

Primary Outcome (intent-to-treat analysis)	Overall (N = 76)	Conventional (N = 36)	Study (N = 40)	P-value
A priori clinical outcome Success, n (%)	29 (38)	16 (44)	13 (33)	0.28
Secondary Outcomes	Overall (N = 72)	Conventional (N = 35)	Study (N = 37)	P-value
I-GERQ-R decrease by 6 – n (%)	24/65 (37)	11/31 (35)	13/34 (38)	0.82
Feeding Outcome at Time 2 – n (%)				0.26
PO	51 (71)	27 (77)	24 (65)	
Transition (PO + Tube)	18 (25)	8 (23)	10 (27)	
Tube	3 (4)	0 (0)	3 (8)	
Length of hospital stay – days	108 [82 - 128]	108 [83 - 125]	98 [81 - 132]	0.89
Hospital stay Inception to Discharge – days	25 [11 - 45]	23 [3 - 39]	27 [16 - 47]	0.26
Weight Growth Velocity (GV) – g/day	27.1 (9.4)	26.5 (7.2)	27.6 (11.1)	0.64
Length GV – cm/day*	0.1 (0.1)	0.1 (0.1)	0.1 (0.1)	0.88
Head Circumference GV – cm/day*	0.1 [0.0 - 0.1]	0.1 [0.0 - 0.1]	0.1 [0.0 - 0.1]	0.87
Feeding Method at Discharge – n (%)				0.32
PO	54 (75)	29 (83)	25 (68)	
Transition (PO + Tube)	14 (19)	5 (14)	9 (24)	
Tube	4 (6)	1 (3)	3 (8)	
Oxygen Requirement at discharge – n (%)	16 (22)	9 (26)	7 (19)	0.49
Compliance to Feeding Methods				
Total Fluid Volume (TFV)				
TFV at Inception- #	N/A	150 [147, 152]	150 [149, 156]	0.8
TFV at Time 2- #	N/A	143 [134, 148]*	133 [126, 137]*	<0.001
# days TFV ≤ 140 / kg / day	N/A	10 [2, 26]	22 [11, 31]	0.005
TFV compliance (TFV <140/kg/d for >75% of time)	N/A	9 (26)	27 (73)	<0.001
Position				
Feeding Position, RSL, %	N/A	5 [1, 17]	78 [12, 94]	<0.001
Feeding in RSL >75% of the time, %	N/A	0 (0)	21 (57)	<0.001
Supine Position Post-Prandial, %	N/A	50 [40, 66]	87 [74, 96]	<0.001
Supine Position Post-prandial >75% of the time, %	N/A	7/34 (21)	27/36 (75)	<0.001
Feeding Duration				
% time feed duration >30 min, %	N/A	4 [0, 37]	15 [0, 69]	0.15
Feeding Duration at Inception, min	N/A	23 [17, 41]	30 [19, 34]	0.64
Feeding Duration at Time 2, min	N/A	23 [18, 28]	26 [20, 30]	0.15
Long-term Follow-up†				
Feeding Method at 6 months – n (%)				0.65
PO	36/50 (72)	21/27 (78)	15/23 (65)	
Transition (PO + Tube)	10/50 (20)	4/27 (15)	6/23 (26)	
Tube	4/50 (8)	2/27 (7)	2/23 (9)	
Feeding Method at 1 year – n (%)				0.11
PO	37/44 (84)	20/22 (91)	17/22 (77)	
Transition (PO + Tube)	4/44 (9)	0/22 (0)	4/22 (18)	
Tube	3/44 (7)	2/22 (9)	1/22 (5)	
CCABSID-III				
Cognitive Score <80 – n (%)	9/44 (21)	5/23 (22)	4/21 (19)	1.00
Cognitive Score – #	95 [90 - 105]	100 [90 - 105]	90 [90 - 100]	0.11

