**Table 3. Feeding and I-GERQ-R Outcomes by Feeding Method at Inception**

Outcome	Conventional	Study	P-value
Among those Tube fed at Inception			
Achieved exclusive oral feeding	N = 18	N = 20	
Achieved I-GERQ-R decrease $\geq 6$	11 (61)	7 (35)	0.11
Achieved PO or I-GERQ-R decrease $\geq 6$	7/17 (41)	8 (40)	0.94
Achieved exclusive oral feeding + I-GERQ-R decrease $\geq 6$	14 (78)	13 (65)	0.39
	4/17 (24)	2 (10)	0.38
Among those PO fed at Inception	N = 17	N = 17	
Maintained PO	16 (94)	17 (100)	1.0
Achieved I-GERQ-R decrease $\geq 6$	4/14 (29)	5/14 (36)	1.0
Maintained PO or I-GERQ-R decrease $\geq 6$	16 (94)	17 (100)	1.0
Maintained PO + I-GERQ-R decrease $\geq 6$	4/14 (29)	5/14 (36)	1.0

[figure not shown]
Data presented as n (%).

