## 4.0 Study Endpoints

- Primary Outcome
  - **Clinical outcome of feeding success for those infants transitioning to oral feeds at inception.**
    - The primary endpoint is the feeding success defined as achieving full oral feeds (defined as no need for tube feeds to maintain hydration and nutrition) and/or a  $>/=$  6-point decrease from baseline I-GERQ-R. The time frame is up to 5 weeks after enrollment.
  - **Clinical outcome of feeding success for those infants on full oral feeds at inception.**
    - The primary endpoint is the feeding success defined as maintaining full oral feeds and a  $>/=$  6-point decrease from baseline I-GERQ-R. The time frame is up to 5 weeks after enrollment.
- Secondary Outcomes
  - Clinical Outcomes
    - Length of hospital stay
    - Growth outcomes during the study period and up to 1 year
    - Independent feeding skills over time up to 1 year
    - Respiratory support during the study period and at discharge
    - Developmental outcomes with Bayley's scores at 2 years
    - Individual differences in I-GERQ-R questionnaire
  - Motility Outcomes
    - Mechanisms of aerodigestive clearance and esophageal provocation are evaluated based on esophageal motility studies at inception and after 5 weeks.
  - pH Impedance outcomes
    - 24-hour pH impedance results at inception of study and then 5 weeks later after treatment completed

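### The secondary oral-feeding comparison ignores feeding status at inception, though the protocol plans models that include feeding method; adjusting for it gains precision but leaves non-superiority unchanged

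*Combined protocol and SAP*

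**What the plan says.** Section 4.0 defines the primary composite by feeding status at inception. One definition is headed "Clinical outcome of feeding success for those infants transitioning to oral feeds at inception". For infants already fully oral, "The primary endpoint is the feeding success defined as maintaining full oral feeds and a" drop of at least 6 points in I-GERQ-R. For both, "The time frame is up to 5 weeks after enrollment". The same section lists independent feeding skills up to 1 year as a secondary outcome, without that split.

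Section 3.3 (Aim I, repeated under Intention to treat analysis) plans logistic regression for treatment success, with feeding method (oral vs. tube) as its example of a potential confounder to include. It plans mixed or logistic models, with potential confounders, for the secondary variables.

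The Statistical Methods of the report instead use Fisher or chi-square tests for categorical secondary outcomes, including feeding method. The Study Outcomes text gives "independent oral feeding in 65% (95% CI, 48% - 80%) vs 77% (95% CI, 60% - 90"%), p=0.26. The matching Table 2 row (overall, conventional, study) is "51 (71) 27 (77) 24 (65"). Table 3 splits Time 2 by feeding method at inception, with rows such as "Achieved exclusive oral feeding" and "Maintained PO 16 (94) 17 (100) 1.0". The text cites Table 3 only to say that outcomes did not differ significantly. The Abstract concludes that the bundle is "not superior to PPI alone in improving GERD symptoms or discharge feeding, short-term and long-term outcomes". The Key Points go further and say that restrictive feeding strategies have no effect on symptoms or clinically meaningful outcomes.

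**The concern.** Whether an infant is fully oral at inception almost determines whether it is fully oral at Time 2. Leaving so strong a baseline predictor out of the test has two consequences. The test uses a standard error that includes the large difference between the two kinds of infant, so it loses power. And the single pooled rate averages infants who had oral feeding to gain with infants who could only keep it, so a reader of the text does not see how the first group fared.

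The reading of the feeding result is at stake. A pooled difference of 12 points with p=0.26 looks like little happening. The infants who could change show a larger and very imprecise difference in favour of the conventional arm. That does not establish harm, but it is a poor basis for saying there is no effect.

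**Working it through.** **1. Inputs.** Table 2, Time 2: full oral feeding in 24/37 study and 27/35 conventional. Table 3, tube-fed at inception: 7/20 and 11/18. Table 3, orally fed at inception: 17/17 and 16/17. Table 3's labels are shifted by a line in the extracted text, but the sums fix the assignment: 7+17=24 of 20+17=37, and 11+16=27 of 18+17=35.

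**2. Reported figures reproduced.** 24/37 = 64.9% (Clopper-Pearson 47.5% to 79.8%) and 27/35 = 77.1% (59.9% to 89.6%) match the text. The stated p=0.26 matches the exact test on three categories (oral, transition, tube), 0.264. The 2x2 chi-square for oral feeding gives 0.252. The tube-fed chi-square gives 0.107, against 0.11 in Table 3.

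**3. Differences (study minus conventional, Newcombe 95% CI).**
- Pooled: 64.9 - 77.1 = -12 points (-32 to +9).
- Tube-fed at inception: 35.0 - 61.1 = -26 points (-51 to +5).
- Fully oral at inception: 100 - 94.1 = +6 points, from one conventional infant.

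Part of the gap between -26 and -12 comes from that one infant. If both arms kept 33/34, the pooled rates would be (7 + 17×33/34)/37 = 63.5% and (11 + 17×33/34)/35 = 78.6%, a difference of -15 points.

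**4. Stratified test on the observed counts (Mantel-Haenszel, no continuity correction).**
- Observed study successes: 7 + 17 = 24.
- Expected: 20×18/38 + 17×33/34 = 9.474 + 16.5 = 25.974.
- Variance: 20×18×18×20/(38²×37) + 17×17×33×1/(34²×33) = 2.426 + 0.250 = 2.676.
- Chi-square = (24 - 25.974)²/2.676 = 1.456, p = 0.23, against 0.25 unstratified.

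The stratified summary difference, with weights 20×18/38 = 9.47 and 17×17/34 = 8.5, is (9.47×(-26.1) + 8.5×5.9)/17.97 = -11 points. Stratifying sharpens the test. It does not replace the stratum estimates.

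**5. Power at the planned 100 infants.** Assumptions: 50 per arm, 25 tube-fed and 25 fully oral in each, 97% (33/34) maintaining in both arms, two-sided 0.05. Simulated power:

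| Oral-feeding rates in tube-fed infants | Pooled chi-square | Stratified by inception status |
|---|---|---|
| 61% vs 35% (observed) | 28% | 42% |
| 40% vs 67% (the design's composite rates, borrowed) | 33% | 45% |

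A closed form shows the source of the gain: power ≈ Φ((D - 1.96×SE0)/SE1). For 61% vs 35%, both tests have D = 0.26/2 = 0.13 and true SE1 = √[25×(0.61×0.39 + 0.35×0.65 + 2×0.97×0.03)/2500] = 0.072. The tests differ in the null SE.
- Pooled: SE0 = √(0.725×0.275×2/50) = 0.089, power about 27%.
- Stratified: SE0 = √[0.25×(0.48×0.52 + 0.97×0.03)×(2/25)×(50/49)] = 0.075, power about 40%.

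With 90% to 100% maintaining, the same formula gives 26% to 27% pooled and 34% to 44% stratified. At the sizes actually analysed (20 and 18 tube-fed, 17 and 17 fully oral), simulation gives about 24% pooled and 33% stratified for 61% vs 35%.

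**6. Later rows.** Full oral feeding, study vs conventional, was 25/37 vs 29/35 at discharge, 15/23 vs 21/27 at 6 months and 17/22 vs 20/22 at 1 year. None is split by inception status.

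**The case against.** The strongest reply is that no rule was broken, nothing was hidden and nothing changes. Much of this stands. Table 3 gives both strata for Time 2 with counts and p-values, and the text cites it. Neither the pooled nor the stratified test is significant, and the study arm is numerically lower either way, so the Abstract's non-superiority statement holds. The trial was not powered on this outcome, and randomisation was stratified by acid reflux index and birth gestation, not feeding status. Section 3.3 also leaves room for argument. Its own list of secondary variables does not name oral feeding, which comes from Section 4.0, and it does not say that feeding method means the value at inception. For an oral-feeding outcome, though, inception status is the only form of that covariate that makes sense.

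A reader might infer four stronger things that the documents do not support.
- That Section 4.0 requires the achieve/maintain split here. It sets that split for the primary composite only.
- That the study arm did 26 points worse under the Section 4.0 definition. For transitioning infants that definition also counts an I-GERQ-R response, and Table 3 gives 13/20 vs 14/18, -13 points, p=0.39. The 26 points belong to one component in one subgroup.
- That this is the trial's headline result. The headline is the composite, 33% vs 44%.
- That pooling nearly halves power. That sets the pooled test against the tube-fed subgroup alone. Like for like, 42% to 28% is a loss of one third (14/42), and 45% to 33% about a quarter (12/45).

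Dilution at discharge and later is plausible but not shown. The 33/34 ceiling is documented only at Time 2, and the inception status of the 50 and 44 infants followed to 6 months and 1 year is not given.

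**Conclusion.** The concern holds as a point about precision and reporting. The secondary oral-feeding outcomes were tested without feeding status at inception, a strong predictor already held for every infant and the protocol's own example of a covariate. At 100 infants the omission costs roughly 12 to 14 percentage points of power, assuming half are fully oral at entry, 97% of them maintain and there is no effect among them. The 61% vs 35% scenario is taken from the observed result, so its power figures illustrate the loss and are not design values. Power is low with either test.

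On the actual data p moves from 0.25 to 0.23 and the finding of non-superiority is unchanged. What does not follow is the absence of an effect claimed in the Key Points. In the infants who could gain oral feeding the estimate is -26 points, with an interval from -51 to +5. That interval includes zero, so it does not show harm either.

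**What to change.** Analyse full oral feeding at Time 2, discharge, 6 months and 1 year with a Mantel-Haenszel test stratified by feeding status at inception, or a logistic model adjusted for it. With almost no failures among infants fully oral at entry, the stratified test is the safer choice at Time 2, and an interaction term could not be estimated reliably there.

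In the Study Outcomes text, beside the pooled rate, give achieved (7/20 vs 11/18) and maintained (17/17 vs 16/17), each with the difference and its interval. Split the discharge and later rows of Table 2 in the same way where inception status is known. State that the p=0.26 printed beside the oral-feeding rate matches a three-category test. Reword the feeding conclusion in the Key Points as superiority not shown, with an imprecise estimate.

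The cost is re-tabulation of data already held. The stratum estimates come from small groups (38 and 34 infants at Time 2, fewer later) and should be labelled imprecise, so that the 26 points are not over-read.

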## **RESULTS**

### *Participant Characteristics*

Screening, recruitment and follow-up of subjects occurred between August 2012 to October 2018, and data was locked May 2019. Recruitment ended to allow for clinical outcome analysis. *From the 688 infants assessed for eligibility, ARI was: normal (<3%) in 246 (36%), indeterminate (3-7%) in 169 (25%), and abnormal (>7%) in 273 (40%). Study enrollment, randomization, and primary outcome analysis are described in the CONSORT diagram (Fig 1). Demographic and clinical characteristics at allocation were not significantly different in both groups (Table 1).* Frequency (%) of GERD referral reasons were for respiratory concerns (apnea/bradycardia/desaturation, airway management, or suspected aspiration) in 54%, feeding concerns (poor oral feeding or intolerance) in 47%, and GERD type symptoms (arching/irritability or emesis) in 25% (note proportions do not add to 100 due to providers being able to list multiple reasons for referral). Reasons for referral did not differ between conventional and study groups (all  $P>0.05$ ). Proportion of milk types (exclusive breast milk: exclusive formula: combination of formula and breast milk, %) were not different between groups: 19: 67: 14 in conventional vs 18: 53: 3 in study groups ( $P=0.24$ ). Of those formula fed (28 in conventional group, and 29 in study group) proportion of formula types (hydrolyzed: gentle: low lactose: preterm: standard, %) were: 4:7:4:75:10 in conventional vs 10:10:0:69:10 in study groups ( $P=0.84$ ). Caloric density ranged

from 19 cal/oz to 30 cal/oz, and the proportions (%) (19: 20: 22: 24: 27: 30 cal/oz) for conventional (11: 31: 33: 19: 6) and study groups (8: 20: 30: 35: 3) did not differ ( $P = 0.47$ ). Breast milk intake in both groups was 40% at inception ( $P=1.0$ ), and the caloric density (cal/oz) for the conventional vs. study groups was 24 [22-25] and 24 [22-27] respectively ( $P=0.41$ ) For conventional and study groups respectively, acid suppressive dose (mg/kg/dose BID) was 0.75 [0.75 – 0.75] vs 0.75 [0.75 – 0.75],  $p=0.27$  upon initial dose, and 0.75 [0.75 – 1.0] vs 1.0 [0.75 – 1.0],  $p=0.09$  at follow-up.

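### The one symptom item reported as differing between arms is labelled Time-1, but its percentages fit 31 and 34 infants, not the 35 and 37 scored at inception

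*Combined protocol and SAP*

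**What the plan says.** The paragraph headed Primary and Secondary Clinical Outcomes reports no differences in the vomiting, regurgitation and crying items "within the group or between the groups across maturation for these individual symptoms, except for symptoms with emesis". For that item the response split (never, rarely, sometimes, often, always, in percent) "was 16:16:42:19:6 for conventional group at Time-1 vs 18:18:29:0:35 for study group at Time-1", with p<0.01. No denominator is printed for the item.

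The same paragraph gives the numbers scored on the whole questionnaire: "At inception: positive I-GERQ-R was 19/35 (54%) in the conventional group vs 24/37 (65%) in the study group", and "At Time-2: positive I-GERQ-R prevalence was 9/31 (29%) in the conventional group vs 13/34 (38%) in the study group". In Table 2 the row "I-GERQ-R decrease by 6", which needs a score at both times, is 11/31 and 13/34. Table 1 shows 36 and 40 infants randomised.

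In the protocol, section 4.0 Study Endpoints lists "Individual differences in I-GERQ-R questionnaire" among the secondary outcomes, and section 3.3 Statistical procedures plans Holm's method for multiple comparisons. The Statistical Methods section of the report names Fisher's exact or chi-square tests for categorical secondary outcomes.

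**The concern.** A comparison labelled Time-1 should describe the 35 and 37 infants scored at inception. If it describes 31 and 34, the reader cannot tell which infants were compared, or when.

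The answer decides what the result means. At Time-1 it is a baseline imbalance in one item, on a set that leaves out (35 − 31) + (37 − 34) = 7 of the 72 infants scored at entry. At Time-2 it is a post-treatment difference in an outcome that the protocol lists as secondary. It is the only item result reported as significant. The p-value also appears to come from a test that ignores the order of a five-level frequency scale.

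**Working it through.** **Inputs.** Percentages 16:16:42:19:6 and 18:18:29:0:35, p<0.01, inception n of 35/37 and Time-2 n of 31/34, all from Primary and Secondary Clinical Outcomes; paired-score n of 31/34 from Table 2; randomised n of 36/40 from Table 1.

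**Step 1: the neighbouring figures.** Uncorrected chi-square reproduces the printed values: 19/35 vs 24/37, p=0.36; 9/31 vs 13/34, p=0.43; 11/31 vs 13/34, p=0.82. The printed denominators are therefore sound.

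**Step 2: which n can give the item percentages.** For each n from 10 to 40, look for whole counts that sum to n and lie within 0.5 point of all five percentages.

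| Arm | n that fit | Counts |
|---|---|---|
| Conventional | 31 only | 5, 5, 13, 6, 2 (16.1, 16.1, 41.9, 19.4, 6.5%) |
| Study | 34 | 6, 6, 10, 0, 12 (17.6, 17.6, 29.4, 0, 35.3%) |
| Study | 17 | 3, 3, 5, 0, 6 |

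Why the other candidates fail:
- n=35: 5/35 = 14.3% and 6/35 = 17.1%, so 16% is out of reach.
- n=36: 6/36 = 16.7%, which rounds to 17%.
- n=37: 6/37 = 16.2% and 7/37 = 18.9%, neither rounding to 18%; 10/37 = 27.0% and 11/37 = 29.7%, neither rounding to 29%.
- n=40: 11/40 = 27.5% and 12/40 = 30.0%, so 29% is out of reach.

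Cutting off decimals instead of rounding does not rescue 35 or 37. At 35 no count gives 16-point-something percent. At 37 the counts would be 7 + 7 + 11 + 0 + 13 = 38, not 37.

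**Step 3: reproduce the printed p.** For 31 vs 34 the column totals are 11, 11, 23, 6 and 14, of 65 infants. Expected conventional counts (column total × 31/65) are 5.25, 5.25, 10.97, 2.86 and 6.68; expected study counts are 5.75, 5.75, 12.03, 3.14 and 7.32. The sum of (observed − expected)²/expected is 13.61 on 4 df, p=0.0087. The exact test (Fisher-Freeman-Halton, by simulation) gives about 0.005. Both agree with p<0.01. For 31 vs 17, chi-square is 9.26 and p=0.055, which contradicts p<0.01. That leaves 34.

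**Step 4: use the order of the scale.** There are 31 × 34 = 1,054 between-arm pairs. The conventional infant has the worse response in 30 + 156 + 132 + 44 = 362 pairs, and 30 + 30 + 130 + 0 + 24 = 214 are ties. The rank-sum statistic is 362 + 214/2 = 469, against 1,054/2 = 527 under no difference; p is about 0.43.

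| Cut | Study | Conventional | Fisher p |
|---|---|---|---|
| Always | 12/34 (35%) | 2/31 (6%) | 0.006 |
| Often or always | 12/34 (35%) | 8/31 (26%) | 0.43 |
| Sometimes or worse | 22/34 (65%) | 21/31 (68%) | not tested |

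The arms differ in shape: *often* is 0/34 vs 6/31 and runs against *always*.

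**The case against.** The strongest reply is that the Time-1 label may be right. 31 and 34 are also the numbers with a score at both times. The sentence covers within-group comparisons over time, which need both scores, and the label is printed separately for each arm. A baseline comparison in the paired set would give exactly these figures, as could missing item data at entry. This stands: mislabelling is not shown. It does not remove the problem, because the text states no such restriction and the adjacent inception figures use 35 and 37.

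A reader might infer that a significant harm of the bundle has been relabelled as baseline. The documents do not support that. The denominators cannot separate the readings, the ordered test shows no overall shift, and the exception is printed openly with its p-value. The contrast in *always* was picked after seeing the data. The size of the Holm family is not stated either. With the four named items the first threshold is 0.05/4 = 0.0125, which 0.0087 meets; if each had four within- and between-arm comparisons (an assumption), it is 0.05/16 = 0.003, which neither 0.0087 nor 0.005 meets.

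A reader might also infer that the Abstract is false where it says "secondary outcomes did not significantly differ (p>0.05", or that "Demographic and clinical characteristics at allocation were not significantly different in both groups" is contradicted. Neither follows. The Abstract names growth, length of stay, oxygen and Bayley outcomes, not items; the allocation sentence cites Table 1, which holds no I-GERQ-R item.

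**Conclusion.** The point holds as a reporting error of minor to moderate weight. The percentages labelled Time-1 describe 31 and 34 infants, so either the time label is wrong or the analysis set is undeclared. This assumes only that the five percentages in each arm share one denominator and were rounded or truncated to whole numbers. Settling on 34 over 17 also relies on the printed p<0.01.

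Which explanation is true cannot be decided from the documents. Under either, the evidence for a difference depends on the test: 0.0087 when order is ignored, about 0.43 when it is used. The primary result (13/40 vs 16/36) and the total-score results are unaffected.

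**What to change.** - Check the item data. Print the item by arm with its n at each time point, using all available infants at Time-1 and all available at Time-2.
- Correct the time label, or state that the Time-1 comparison was limited to infants with both scores or with item data.
- Replace the unordered test with a rank-based one, and keep the full five-level distribution so that the opposing *often* and *always* counts remain visible.
- If the data are Time-2, describe the result as a post-treatment item difference in a protocol-listed secondary outcome, apply the planned Holm adjustment with the family of tests stated, and qualify the Discussion's statement that pre-assigned secondary outcomes did not differ.
- If the data are Time-1, describe it as a baseline imbalance in one item.

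The cost is one tabulation of data already collected, one further test, and two or three corrected sentences.
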